weight stratum. The numbers on these envelopes correspond to those on the randomization log maintained at the CC. If more than one participant is to be randomized at the same time, the clinic will arrange a listing of these subjects, first by weight stratum, if applicable, and then by ID order. The envelopes will then be opened in this order and the assignment communicated to each subject. Otherwise, randomization assignments are given in the order of the participants' appointments. Whenever a random assignment is made, the envelope, sealed (if the clinic staff obtained the subject's assignment from the CC) or unsealed (if the CC staff was unavailable), will be returned to the CC as confirmation of the randomization process. As further confirmation, the clinic will call the CC as soon as possible (usually the next working day) to report each intervention assignment made using the back-up system.

Once the assignment has been communicated to the participant, he or she is considered to be officially randomized, and every effort will be made to obtain complete follow-up information for the duration of the trial. Active intervention will begin at the discretion of the clinic; however, the target goal is to have all lifestyle participants attend their first intervention group meeting within 30 days of randomization. Any individual who fails to appear for his or her status review visit may be rescheduled for a new status review visit at the discretion of the clinic staff, as long as the visit is within 60 days of SV3.

2. Clinics Testing Supplements Only

At the conclusion of SV3, participants who are deemed provisionally eligible to continue in the trial will be given run-in calendar packs and a 24-hour urine kit and scheduled for a status review visit in four to eight weeks (28 to 56 days). All information necessary to assess eligibility will be sent to the CC for review and verification, and the CC will determine eligibility within 5 working days of receipt of SV3 data and send an eligibility status report to the clinic. The clinic will inform participants to discontinue their pills if their status is reported as ineligible and will take measures to clarify information if the CC reports an ambivalent status. Approximately 3-5 days in advance of their scheduled status review visit, eligible participants will be contacted to remind them of their appointment and instructed to bring their 24-hour

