urine collection and all their calendar packs to the upcoming visit. At the status review visit, clinic personnel will assess pill compliance by calculating the total number of days since the last visit (SV3) and the number of pills taken (by pill count) and determine if the participant is eligible for randomization. Only participants who have taken 2/3 of their pills will be included in the trial. Compliance information will be recorded on the status review form.

Each clinic will have the option of "rerunning" participants who have failed to meet the run-in compliance test but are still willing to continue. Those whose run-in is extended will be given additional calendar packs and asked to return in about 6 weeks. At that time, compliance will be assessed again; participants demonstrating poor compliance or a desire to discontinue will be excluded from the trial.

For participants who successfully complete the run-in compliance test, randomization will proceed as described above, by phone contact between clinic and CC and envelope back-up system if contact is not possible. The sealed or unsealed envelope corresponding to the assignment will be forwarded to the CC along with the status review form. At the conclusion of the visit, randomized participants will be given their assigned intervention pills. To ensure that blindness is maintained, all supplements assignments and pill identification will be by code.

3. Clinics Offering Both Lifestyle and Supplements Interventions

Participants who are deemed provisionally eligible at the conclusion of SV3 will at that time be assigned, using a random procedure, to either the lifestyle or supplements track. This assignment is determined using a system of sealed envelopes, opened in numerical order, as described above. No direct contact with the CC is required for preliminary allocation. In this manner, participants will be told at the earliest possible moment which general type of intervention they may receive. Those assigned to the lifestyle track and willing to continue will proceed, as for other lifestyle participants, to a status review visit within 10 to 60 days later. Those assigned to the supplements track who are willing to continue will proceed, as for other supplements participants, to complete the run-in phase.

FOLLOW-UP SCHEDULE

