- Pills will be packaged in convenient calendar packs.
- b. Individual instruction regarding administration of the supplements, positive reinforcement, and/or discussion of suspected side effects and what to do about them will be provided by the participant's health counselor, preferably a nurse with experience in reinforcing medication compliance among patients.
- c. Calendar packs will be dispensed in such a manner that the participant will have a sufficient supply of pills to last from one follow-up

visit to the next. An additional card will be dispensed at the beginning of each phase to serve as a reserve pack in case a visit is missed or a card lost.

d. At the beginning of the trial each participant will be provided with a set of study guidelines as an aid to compliance. The guidelines will cover such topics as what to do if calendar cards are lost, how and when to take the supplements, what multivitamins and supplements to avoid, and what to do if suspicious of side-effects.

Side Effects

Because of the benign nature of the supplement interventions, we expect a low incidence of side effects attributable to the study pills, although they will be monitored at the follow-up visits. The major potential concern in this regard is the possibility of bleeding problems among individuals assigned to fish oil. Specific procedures pertaining to safety monitoring of the fish oil component are described below.

At each follow-up session a health counselor will discuss with the participant any reported side-effects attributed to the pills. When necessary, the participant will be referred to a licensed physician on the clinic staff who will respond to each individual case using his or her best clinical judgment. In general, participants will be advised to seek medical attention from their own physician as needed and may alter their participation in the light of such counsel. Every effort will be made to maximize compliance consistent with the health and welfare of the participant.

The following procedures have been adopted to monitor the safety of those taking fish oil supplements.

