a. Prior to Stage 2, individuals with a bleeding history will be identified based upon responses to the Supplements Form administered at SV3, SRV, 6 weeks, 13 weeks, and 26 weeks and reviewed by a clinic physician. Those individuals identified by the clinic physician as having a potential bleeding disorder based upon responses to the follow-up forms, will be asked to undergo evaluatory tests for

bleeding time, platelet count and VWF level for possible exclusion from Stage 2 based upon a history of recurrent abnormal bleeding.

- b. Individuals identified by the clinic physician as having a potential bleeding disorder, who do not wish to submit themselves to testing, will be excluded from Stage 2.
- c. During Stage 2, individuals assigned to the fish oil component who develop a bleeding history based upon responses to the Supplements form administered at 6 weeks and 13 weeks of Stage 2 or other self-reports will have their case reviewed by a clinic physician. If in the judgement of the physician it is clinically warranted, the individual will be asked to undergo tests immediately to evaluate the bleeding problem. Participants will be asked to discontinue their pills for the duration of the trial if, in the opinion of the clinic physician, the tests reveal an abnormal bleeding problem or if the participant refuses to undergo the recommended evaluation procedures.

ASCERTAINMENT OF ENDPOINTS

Both primary and secondary outcomes for TOHP are determined from measurements and laboratory tests taken at follow-up visits; therefore, ascertainment of endpoints is relatively simple and straightforward. Outcome measurements will be made by data collectors blinded to the treatment assignment of participants and not involved in delivering any lifestyle intervention. Due to the subjective nature of BP measurement, it is particularly important that the BP observers are not involved in any way with the delivery of any intervention and have no access to intervention-specific data. Insofar as possible, data collection visits should take place on different days and at different locations from intervention visits so that those in the active intervention groups do not become more habituated to the data collection environment than those in the comparison group.

Ascertainment of Blood Pressure

The outcome of primary interest, for which the sample size and power calculations were performed, is diastolic BP; a major secondary endpoint is

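### The bleeding screen for entry to the fish oil stage uses no Supplements Form later than Stage 1 week 26, about 15 to 32 weeks before Stage 2 randomization

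*Protocol*

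**What the plan says.** All references are to the Protocol.

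- **The hazard** (Intervention Methods, Supplements, Side Effects): "The major potential concern in this regard is the possibility of bleeding problems among individuals assigned to fish oil".
- **The screen before Stage 2** (same place, item a): people with a bleeding history are found from "responses to the Supplements Form administered at SV3, SRV, 6 weeks, 13 weeks, and 26 weeks and reviewed by a clinic physician". Those the physician flags are asked to have tests of "bleeding time, platelet count and VWF level for possible exclusion from Stage 2 based upon a history of recurrent abnormal bleeding".
- **Refusal of testing** (item b): flagged people "who do not wish to submit themselves to testing, will be excluded from Stage 2".
- **During Stage 2** (item c): review is triggered by "responses to the Supplements form administered at 6 weeks and 13 weeks of Stage 2 or other self-reports". Because item c names the Stage 2 forms separately, the weeks in item a are Stage 1 weeks.
- **Other routes out of Stage 2** (Supplements, Clinic Procedures): Stage 2 is open to every Stage 1 participant. People with disqualifications other than low blood pressure are randomized in their own stratum and left out of the main analysis. Items a and b are therefore the only stated exclusion from Stage 2 based on bleeding.
- **General enquiry**: the Side Effects section says of side effects, "although they will be monitored at the follow-up visits". Safety Monitoring has exclusion conditions asked about at each follow-up visit. Table 3, which is broken in the available text, appears to show the Health Experience form at about F05.

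**The concern.** Item a decides who is reviewed, tested and possibly kept off fish oil. The information it uses stops at Stage 1 week 26, yet fish oil is assigned only after the rest of the Stage 1 termination visits, the washout and the re-eligibility visits. Blood pressure eligibility is re-established at those visits and new baseline data are collected, but item a lists no renewed bleeding form.

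A participant who develops a bleeding history in that interval could be randomized to fish oil without the review and tests that item a intends. The first Supplements Form listed under item c comes six weeks into Stage 2, when fish oil is already being taken, unless a self-report comes sooner.

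**Working it through.** The protocol gives no figure for this interval, so it has to be built from the visit windows.

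**Inputs**
- Week 26 is taken as the Stage 1 6-month visit.
- Stage 1 termination: three visits, so two gaps of 7 to 30 days (14 to 60 days). Clinic Procedures starts them at the 6-month visit, so the last falls 14 to 60 days after week 26. Follow-Up Schedule starts them about 14 days earlier, so the last falls 0 to 46 days after week 26.
- Washout: about three months, taken as 91 days (assumption).
- Re-eligibility (Clinic Procedures): three visits, two gaps of 7 to 30 days (14 to 60 days).
- Stage 2 randomization (F08): 0 to 10 days after the last eligibility visit.

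**Gap = termination offset + washout + eligibility visits + days to randomization**

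| Timing of termination visits | Shortest | Longest |
|---|---|---|
| Follow-Up Schedule | 0 + 91 + 14 + 0 = 105 d (15.0 wk) | 46 + 91 + 60 + 10 = 207 d (29.6 wk) |
| Clinic Procedures | 14 + 91 + 14 + 0 = 119 d (17.0 wk) | 60 + 91 + 60 + 10 = 221 d (31.6 wk) |

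Taken together the range is 105 to 221 days, about 15 to 32 weeks. The top end stacks every window at its maximum. A 12-week washout (84 days) shifts the range to about 14 to 31 weeks.

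**If the eligibility visits fall inside the three months**, their term drops out:
- Follow-Up Schedule timing: 0 + 91 + 0 = 91 d (13.0 wk) to 46 + 91 + 10 = 147 d (21.0 wk).
- Clinic Procedures timing: 14 + 91 + 0 = 105 d (15.0 wk) to 60 + 91 + 10 = 161 d (23.0 wk).
- Range: about 13 to 23 weeks.

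**Effect of a form at F05.** The form would then be 14 + 0 = 14 to 60 + 10 = 70 days before randomization. It would cover (105 − 14)/105 = 87% of the shortest gap and (221 − 70)/221 = 68% of the longest.

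**People affected.** The protocol gives no bleeding rate. If 0.1% to 1% newly reported a bleeding history in the interval (assumption), that is 0.2 to 2.0 of the 199 estimated fish oil participants in Table 1. This counts new reports. Those who would test abnormal and be excluded would be fewer.

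**Cost in power.** With SD 6.17 and a 2 mm Hg difference, power = Φ(2 / [6.17 × √(1/n₁ + 1/n₀)] − 1.96). For 199 against 203 this is Φ(2/0.615 − 1.96) = .90, which reproduces Table 12. If 1% were excluded, 197 against 201 gives Φ(2/0.619 − 1.96) = .90 to two decimals.

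**The case against.** **Item a suits its stated target.** It looks for a recurrent tendency, and five forms from SV3 to week 26 already span about 30 to 34 weeks (28 to 56 days of run-in plus 26 weeks). Stopping there also leaves the washout free for review and testing, although the protocol does not give that as the reason. This stands, and it is a main reason the priority is low. It does not help with a history that begins or becomes recurrent after week 26.

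**The interval is not unsupervised.** Participants are seen at the re-eligibility visits. A health counselor discusses reported side effects at follow-up sessions and can refer to a physician. Questions on exclusion conditions would touch criterion 11 (chronic gastrointestinal disease, including ulcer and colitis) and criterion 13 (interfering drugs, including anticoagulants). Item b does not itself restrict how the physician identifies someone. All of this may catch some cases. However, none of it is stated to feed item a's review or tests, a bleeding disorder as such is not a listed exclusion, and Clinic Procedures would otherwise keep a disqualified person in Stage 2 in a separate stratum.

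**The form's full schedule is not visible.** Table 3 as available has no row for the Supplements Form, and form-level detail may be in the Manual of Operations. A reader might infer that the form is definitely not given at F05 to F07. The documents do not show that. They show only that item a does not name it there as a basis for the screen.

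**The contrast with Stage 1 entry is weak evidence.** The form is used at SRV, the Stage 1 randomization visit ("At the conclusion of the visit, randomized participants will be given their assigned intervention pills"). A reader might infer that a form on the day of randomization was meant as a rule for each stage. The protocol does not say so.

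**Conclusion.** The point holds as a low-priority safety improvement. Item a's information is about 15 to 32 weeks old at Stage 2 randomization, or about 13 to 23 weeks if the eligibility visits sit inside the washout. Bleeding that arises in that interval is outside the responses the physician is directed to review. The interval rests on a washout of about 91 days and on the stated visit windows. The count of people affected rests on an assumed rate and is small.

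Three stronger readings are not supported:
- *Fish oil is taken without monitoring in the gap.* Participants take placebos of their Stage 1 agent during the washout, and fish oil starts only after Stage 2 randomization.
- *The randomized comparison is biased.* The screen precedes Stage 2 randomization and applies before assignment is known. The primary analysis and its error rate are unaffected.
- *Item c needs a further form at the Stage 2 6-month visit (F13) for the same reason.* Item c's remedy is to stop the pills, which is largely moot at the end of treatment, and general side-effect questions and self-reports already cover those weeks to some extent.

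**What to change.** In item a, add the first re-eligibility visit (F05) to the listed administrations of the Supplements Form, and state that physician review is to be completed before Stage 2 randomization (F08). F05 is preferable to the last eligibility visit (F07) because it leaves at least 14 days for review and the named tests, against 0 to 10 days from F07.

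The cost is one more use of an existing form at a visit already scheduled, for about 207 + 199 + 203 = 609 estimated entrants (Table 1). A few more people may be tested or excluded before randomization. No new visit is needed, and fish oil power at 2 mm Hg stays at .90 even if 1% are excluded.

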Subjects will keep food diaries as an essential component of the weight loss/exercise regimen. The food diary assignment in the first week will be two days of diaries increasing to five or more days per week by the fourth week of intervention. To increase adherence to the food diary protocol, subjects' food diaries will be reviewed by group leaders and returned with comments at the next meeting.

Each subject will be weighed privately before each session by a staff member. Records of weight change and exercise will be kept in the form of a graph with weight plotted in terms of change from baseline and exercise plotted as a bar graph in terms of minutes of exercise per day. Subjects will also be given feedback on their level of fitness based on a sub-maximal exercise test which will be administered at baseline, at the

end of the active intervention phase (when the amount of weight loss is anticipated to be maximal), and at termination of the study.

Stress Management

1. Objectives

The overall objective of the TOHP stress management program is to reduce the stress level in its participants. Individual goals include achieving formal relaxation (7 minutes or more) at least four times per week, as well as attendance at a minimum of 8 out of 10 of the initial weekly sessions and a minimum of 15 out of 20 of the first year's sessions. It is also expected that individuals will be rated at 2 or lower on the 10-point Behavioral Relaxation Rating Scale (one is completely relaxed) by interventionists. Group objectives will be a minimum of 70% of the individuals formally relaxing at the level described above, 70% of the individuals attending 8 of 10 of the initial weekly sessions, a minimum of 65% attending 15 of 20 of the first year's sessions, and a minimum of 70% of the individuals rated by interventionists at 2 or lower on the 10-point Behavioral Relaxation Scale.

2. Approach

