Initiation of medications for reasons other than elevated BP may also result in BP lowering which may confound the effects of the study intervention. For this reason, participants and their private physicians will also be asked to inform study staff and consider agreeing to a set of termination BPs prior to starting a drug with hypotensive effects, if such a delay is consistent with good medical practice. Examples of such medications might be diuretics, beta-adrenergic blockers, calcium channel blockers, and other drugs with hypotensive effects which may be prescribed for a wide variety of medical conditions other than hypertension.

b. Participants Who Move Out of the Study Area

If a participant moves out of the study area beyond a distance that allows continued participation to be practical, every attempt should be made to obtain a set of termination BPs prior to the move. Those who know that they plan to move during the course of the study will be excluded from participation. However, participants should also be reminded during the course of the study to inform the study staff of an upcoming move as soon as possible so that the nine termination BPs can be obtained prior to the move. After obtaining these nine readings, if a participant in one of the supplements groups expresses a desire to continue on the supplements for the duration of the trial and agrees to travel back to the study center for the nine termination readings at the end of the study, continued participation can be tried. This seems less realistic for the lifestyle groups where ongoing contact with the study staff may be more important.

If a participant is moving to a location convenient to another TOHP clinical center, the option of transferring should be considered. Any such transfer should be coordinated by the CC with the full cooperation of both the old and new clinical centers. If the participant is willing and the new clinic offers the same intervention as the original center, it may be possible for that individual to

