continue full participation in the trial. If not, the participant should be encouraged to attend the new clinic for scheduled data collection visits. Transfers who are in the supplements arm of the trial should be maintained on study pills without interruption, with a sufficient number of pill packs dispensed by the original center. Data from transfers will be stored and analyzed under the participant's original study ID number with the other data from the original clinical center.

Temporary absence from the study area for more than 3 months should be preceded, if possible, by obtaining the nine termination BPs. For example, a participant who plans to go to Florida for 3 months in the winter should have a set of termination BPs obtained prior to leaving. If the participant agrees to continue following his or her study program (both intervention and comparison groups) faithfully during this absence and plans to be back in the study area at least two months prior to scheduled termination, continued participation can be attempted. However, if the participant fails to return for subsequent BP measurements, then the set of measurements obtained prior to his/her departure will constitute the terminating BP.

Ascertainment of Secondary Endpoints Specific to Interventions

In addition to BP endpoints collected on all participants in the trial, there are also secondary endpoints specific to the interventions being tested. These endpoints will be assessed in participants enrolled in the active intervention group and their corresponding controls. The secondary endpoints to be used in each of the intervention groups are described briefly:

1. Sodium restriction

Secondary endpoints for the sodium-restricted group include urinary sodium excretion and measures of sodium intake as determined from food/nutrient data including food frequency questionnaires and 24-hour diet recalls. Of these measurements, urinary sodium excretion provides the most convincing data because it is not as subject to bias as is self-reported nutrient data. The schedule for collection of 24-hour and overnight urines for measurement of sodium excretion is as described in the sodium intervention

protocol and listed in Table 8 and that for food/nutrient data as described in the chapter on Follow-Up Schedule.

2. Weight reduction

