The primary outcomes of interest for the lifestyle interventions is the difference between changes in mean DBP from baseline to 18 months between the intervention and comparison groups, with the BP for each participant being determined from nine readings (three readings at each of three visits). The primary endpoint for the supplement interventions is change in DBP from baseline to six months. In the crudest level of analysis, mean change in DBP in each of the actual intervention groups with the control group will be compared in the context of the one-way analysis of variance. At a second level, mean change in DBP between each of the active intervention and control groups will be compared after controlling for clinic. This will be accomplished using multiple regression methods introducing dummy variables for

clinic and intervention group. In addition, more refined analyses will be performed to adjust for other covariates, such as mean initial DBP, age, and sex.

Secondary endpoints in the trial, including changes in SBP and the development of hypertension, will also be examined. The former will be evaluated in the same manner as changes in DBP described above. The development of hypertension will be defined as either going on antihypertensive medications during the course of the trial or attaining a mean DBP greater than or equal to 95 mm Hg based on nine readings over three visits at any point in the trial.

While change in DBP from baseline to termination is the primary outcome of interest, there will also be the opportunity to examine BP measurements taken throughout the follow-up period. In particular, slopes of BP over time will be compared based on available data per participant. Slopes in different treatment groups will also be compared using analysis of variance and regression methods as discussed above. More sophisticated methods of longitudinal data will be utilized to characterize more complex changes in BP over time (105-107). In addition, BP change from baseline to the 12-month follow-up point for lifestyles interventions will also form the basis for planning for Phase II of TOHP.

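### Lifestyle movers are not offered the return visit for end-of-study BP that supplements movers get, for a reason that concerns program delivery rather than measurement

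*Protocol*

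**What the plan says.** The relevant text in the Protocol is as follows.

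- **Permanent moves, all groups** (Ascertainment of Endpoints, 3b): "every attempt should be made to obtain a set of termination BPs prior to the move".
- **Supplements movers** (same item): after that set, if the participant wishes to stay on the pills and "agrees to travel back to the study center for the nine termination readings at the end of the study, continued participation can be tried".
- **Lifestyle movers** (next sentence): "This seems less realistic for the lifestyle groups where ongoing contact with the study staff may be more important".
- **Moves near another TOHP center** (same item, all groups): a transfer is considered, and if the new clinic cannot continue full participation, "the participant should be encouraged to attend the new clinic for scheduled data collection visits".
- **Temporary absence of more than three months** (same item): participants in intervention and comparison groups may continue. Only if the person does not come back for later readings, "then the set of measurements obtained prior to his/her departure will constitute the terminating BP".
- **Primary outcome, lifestyle** (Data Analyses): "the difference between changes in mean DBP from baseline to 18 months between the intervention and comparison groups".
- **Follow-up after randomization** (Randomization, section 1, lifestyle clinics): "every effort will be made to obtain complete follow-up information for the duration of the trial". Ascertainment of Blood Pressure likewise treats complete BP data on every subject through the trial as crucial.
- **Lifestyle controls** (Study Design): after orientation they come to the clinic only for data collection.

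**The concern.** The ground for treating lifestyle movers differently is that they need contact with staff. That bears on whether an intervention can be kept going at a distance. It does not bear on whether nine BP readings can be taken at 18 months, and it does not apply to controls, who receive no program.

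A clinic that follows item 3b as written would probably take the pre-move set and not pursue an 18-month set from a lifestyle participant who moves far away. The item sets no minimum time since randomization, so the reading can come from any point on the intervention course. The weight-loss section expects the largest loss at the "end of the active intervention phase (when the amount of weight loss is anticipated to be maximal"), so a set taken then would describe the peak effect and not the lasting one. At the other extreme, the first group meeting is targeted within 30 days of randomization, so a very early set could precede the program.

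At stake are 18-month primary-endpoint readings from participants who might have been willing to give them, and some drift in the meaning of the lifestyle contrast from effect at 18 months to effect at whatever time people left. Ascertainment of Blood Pressure adds to the ambiguity by describing the main endpoint as change from baseline to termination, whereas Data Analyses fixes it at 18 months.

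**Working it through.** **1. Which lifestyle movers are affected**

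| Situation | What the Protocol provides | 18-month readings kept? |
|---|---|---|
| Moves near another center | Transfer, or data-collection visits there | Yes, if the person attends |
| Temporary absence | Pre-departure set used only if the person does not return | Yes, if the person returns |
| Permanent move elsewhere, supplements | Pre-move set, plus the option to travel back | Own six-month endpoint kept if the person returns |
| Permanent move elsewhere, lifestyle | Pre-move set; return called less realistic | Probably not |

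Only the last row is the problem. A lifestyle participant who moves after the 18-month visits already has the primary reading.

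**2. The plan's own figure**

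Inputs for weight reduction: 308 active and 232 control (Table 12); SD of 18-month change 6.36; two-sided alpha 0.05; target difference 2 mm Hg (Power Calculations: DBP).

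- SD check: √(2 × 118.85 × (1 − 0.83)) = √40.41 = 6.36.
- Standard error of the contrast: 6.36 × √(1/308 + 1/232) = 0.553 mm Hg.
- Difference for 80% power: (1.96 + 0.842) × 0.553 = 1.55 mm Hg. Table 12 states 1.55.
- Power at 2 mm Hg: Φ(2/0.553 − 1.96) = 0.951. Table 12 states 0.95.

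Both figures reproduce.

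**3. Effect of substituting pre-move readings**

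The Protocol gives no mover rate and no time course of the effect, so both are assumed. Let m be the share of movers, taken as equal in the two arms, and r the effect at the move as a multiple of the 18-month effect. With a true 18-month effect of 2 mm Hg:

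observed difference = 2 × (1 − m + m·r), so shift = 2m(r − 1)

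| m | r = 0 (before program): difference, shift, power | r = 1.5 (assumed peak): difference, shift, power |
|---|---|---|
| 2% | 1.96, −0.04, 0.944 | 2.02, +0.02, 0.955 |
| 5% | 1.90, −0.10, 0.930 | 2.05, +0.05, 0.960 |
| 10% | 1.80, −0.20, 0.902 | 2.10, +0.10, 0.967 |

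The shift runs from −0.20 to +0.10 mm Hg, or −0.36 to +0.18 of the standard error (−0.20/0.553 and 0.10/0.553). With the stronger assumption r = 2, the top end at m = 10% would be +0.20 mm Hg.

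**4. How many people**

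At an assumed 3–8% movers:

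- weight-loss arm: 0.03 × 308 = 9 to 0.08 × 308 = 25;
- high-weight controls: 0.03 × 232 = 7 to 0.08 × 232 = 19.

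The control figure for this contrast is 232. The 589 lifestyle controls in Table 1 include people outside the high-weight stratum and at clinics that do not offer weight loss.

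**The case against.** The case for leaving the text alone has real weight.

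- **Nothing bars a return.** The wording is a remark about realism, and the item covers only moves too far for participation to be practical. A reader might infer that lifestyle movers are excluded or actively discouraged; the text does not go that far. Its conflict with the follow-up commitment in Randomization is a tension, not a flat contradiction.
- **The transfer clause already separates measurement from intervention** for movers near another center. This stands and narrows the problem. It also shows that the Protocol accepts measurement without intervention.
- **Replacement is not stated for permanent movers.** A reader might take the temporary-absence rule as covering them. It does not. Replacement is inferred from the label termination BPs and from the item's place under final BP measurements for early terminators. The inference is reasonable but remains an inference.
- **There is no supplements-versus-lifestyle bias.** A reader might see the unequal offer as biasing a comparison. Those arms are not compared, and active and control lifestyle participants face the same rule.
- **The size is easily exaggerated.** Taking 8% movers, an early effect 2 mm Hg larger than at 18 months, and every move falling in months 3–6 gives 0.08 × 2 = 0.16 mm Hg, which is 0.29 of the standard error (0.16/0.553). If moves were spread evenly over 18 months, one sixth would fall in that window, giving about 0.03 mm Hg. Early and peak readings also pull in opposite directions.
- **Moves before the program starts should be rare.** People who plan to move are excluded at entry, and nine readings need three visits.

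What this does not answer is the stated reason itself. It fails for controls, and it is no ground for forgoing an 18-month reading from an active participant willing to return. The transfer clause does not help those who move elsewhere.

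**Conclusion.** The point holds in a limited form. Item 3b ties end-of-study measurement to continued intervention for lifestyle movers, on a reason that does not concern measurement. Those not near another center are likely to supply only a pre-move set, of arbitrary timing, for an outcome defined at 18 months.

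The consequence is probably small. At an assumed 2–10% movers, with a pre-move effect between nil and 1.5 times the 18-month effect, weight-reduction power stays between about 0.90 and 0.97. The sign of the shift cannot be known without the timing of moves. These figures assume that every mover's pre-move set is used in place of the 18-month value and that movers are equally frequent in both arms. The Protocol settles neither. No conclusion of the trial is likely to turn on this. It merits correction because the remedy is cheap and could recover real primary-endpoint data.

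**What to change.** In Ascertainment of Endpoints, item 3b:

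1. Replace the remark about the lifestyle groups with a sentence that separates outcome measurement from continued intervention. Lifestyle movers, active and control, would be offered the same return for the nine 18-month readings, whether or not they continue the program. The transfer clause stays as it is.
2. State that a permanent mover's pre-move set is dated and used only as a fallback when the 18-month readings cannot be obtained, matching the rule already written for temporary absence. This would also bring the item into line with the 18-month outcome in Data Analyses and the follow-up commitment in Randomization.

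How fallback values are shown in the analysis is ordinary analysis-plan content and is not part of this request.

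The cost is a short change to the text and travel for the few movers willing to return, an arrangement already accepted for supplements. No new measurement procedure is needed. The Protocol does not show how many distant movers would come back, so the gain may be modest.
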